5.1.2.4. The Last Dose Date of Study Drug

When a partial last dose date of study drug is reported, below rules will be used:

- If only the day of the month is missing, then it will be imputed as the last day of the month;
- If both the day and the month are missing, then it will be imputed as the December 31st of the year
- If the imputed last dose date of study drug is later than date of death (if the subject died) / last known alive date (if the subject is not known to die) / EOT date / EOS date, data cut off date, then it will be replaced by the earliest of the above.

If the last dose date of study drug is complete missing, then it will be imputed by the earliest of the above.

5.1.2.5. Initial Diagnosis Date

When a partial initial diagnosis date is reported, below rules will be used:

- If the date is completely missing, do not impute;
- If both the day and the month are missing, then it will be imputed as July 1st of the year;
- If only the day of the month is missing, then it will be imputed as 15th of the month.

If the imputed initial diagnosis date is later than the first dose date of study drug, it will be replaced by the first dose date of study drug.

5.1.2.6. Subsequent Anti-cancer Therapy Date

When a partial subsequent anti-tumor therapy start date is reported, every effort will be made to identify the precedence relationship of starting date of subsequent anti-tumor therapy relative to the reference end date. Below rules will be used:

- If the date is completely missing, subsequent anti-tumor therapy date will be imputed as reference end date + 1;
- If only the day is missing, 15th day will be imputed as the subsequent anti-tumor therapy date;
- If both the day and the month are missing, then July 1st will be imputed as the subsequent anti-tumor therapy;

If the imputed date is earlier than reference end date, then it will be replaced with reference end date + 1, if the imputed date is later than the date of death or last known alive date, it will be replaced with the date of death or last known alive date.

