Subjects who discontinue the study drug due to reasons other than disease progression, death, lost to follow-up, or withdrawal of consent will remain on study and will be followed every 12 weeks (± 14 days) from EOT visit for tumor assessment until disease progression, initiation of new anticancer therapy, withdrawal of consent, lost to follow-up, death, or the end of the study, whichever comes first.

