4.1.3. Treatment Period

Unless otherwise specified, the treatment period is defined as the period prior to or on the date of first administration of study drug to 30+7 days (7-day window only replies to parameters collected by visit) after the date of last administration of study drug or prior to the start of a subsequent anti-tumor therapy (whichever comes first). For safety data, only the assessments/events collected during the treatment period will be summarized.

The worst post baseline is defined as the worst assessments/events during the treatment period including both scheduled and non-scheduled visit.

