Note: An adequate radiologic assessment is defined as an assessment where the Investigator determined radiological response is CR, PR, SD, or PD. If PD and new anti-cancer medication occur on the same day, will assume that the progression was documented first, e.g. outcome is progression and the date is the date of the assessment of progression

Note: The same algorithm for determination of two or more consecutive missing or inadequate assessments can be found in [Section 4.2.1.3](#).

PFS is calculated as (date of progression or censoring as per rules in [Table 5](#) – date of first administration of study treatment + 1)/30.4375. Reasons for censoring are included in [Table 6](#) following the hierarchy.

Table 6 PFS Censoring Reasons and Hierarchy

Hierarchy	Condition	Censoring Reason
1	No baseline nor post-baseline tumor assessments available	No baseline nor post-baseline tumor assessments
2	New anti-tumor therapy started prior to PD	New anti-tumor therapy started prior to PD
4	Two or more consecutive missed or inadequate radiological assessment visits	Two or more consecutive missed or inadequate radiological assessment visits
5	Drops out before end of study, no progression or death, lost to follow-up	No death nor PD, lost to follow-up
6	Drops out before end of study no progression or death, withdrawal by subject from the study	No death nor PD, withdrawal by subject
7	No death nor PD by the time of data cut-off for the analysis	No death nor PD by the time of data cut-off for the analysis

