4.4.1. Adverse Events (AEs)

All AEs will be coded from verbatim text to preferred term (PTs) and grouped by system organ class (SOC) using the Medical Dictionary for Regulatory Activities (MedDRA) version 27.1. AEs will be graded by investigator according to NCI CTCAE v5.0. Missing severity grade will not be imputed.

An AE is considered a TEAE:

(i) If one of the criteria is met:

1. If the onset date is on or after the start of study treatment until 30 days after the last dose or prior to the start of a subsequent anti-tumor therapy (whichever comes first), or if the onset date is missing; or
2. If the AE has an onset date before the start of study treatment, but worsened in severity after the study drug administration (i.e. SAE start date is on or after the start of study treatment until 30 days after the last dose or prior to the start of a subsequent anti-tumor therapy (whichever comes first));

(ii) Beyond 30 days after the last dose or after the start of a subsequent anti-tumor therapy (whichever comes first), treatment-related SAEs will also be considered as TEAEs.

Investigator assessed AEs causality to study drug will be classified as "Related" and "Not Related". An AE with a missing causality will be classified as "Related" to study drug.

Other AE variables include drug-related AEs, COVID-19 related AEs, AEs leading to study drug modifications (i.e. dose interruption, dose reduction, or study drug withdrawal), AEs leading to death, and SAEs.

For AEs which are not on-going, duration of AE (days) is defined as AE end date – AE start date +1; for on-going AEs, the end date will be listed as ‘Ongoing’.

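### A missing or partial start date for subsequent therapy is imputed without checking the progression date, so a documented progression can be censored and the post-dose TEAE window can fall to 0 days

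*SAP*

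**What the plan says.** SAP 5.1.2.6 imputes the start of subsequent anti-cancer therapy in three cases:

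- Fully missing: "If the date is completely missing, subsequent anti-tumor therapy date will be imputed as reference end date + 1". SAP 4.1.1 defines the reference end date as the last non-zero dose, so this is the first day off drug.
- Day missing: "If only the day is missing, 15th day will be imputed as the subsequent anti-tumor therapy date".
- Day and month missing: "If both the day and the month are missing, then July 1st will be imputed as the subsequent anti-tumor therapy".

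The lower bound is: "If the imputed date is earlier than reference end date, then it will be replaced with reference end date + 1". The upper bound is death or the last known alive date. The section's stated aim is to order the therapy relative to the reference end date. No progression or scan date enters.

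The date is then used in several places:

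- **PFS and DoR (Tables 3 and 5, rule 6).** New therapy before PD means censoring at the last adequate assessment on or before the therapy start. The note to both tables settles ties: "If PD and new anti-cancer medication occur on the same day, will assume that the progression was documented first".
- **BOR, waterfall and spider plots (4.2.1.1, 5.2.9.1).** Data are cut at subsequent anti-cancer medication.
- **TEAEs (4.4.1).** The onset period runs "until 30 days after the last dose or prior to the start of a subsequent anti-tumor therapy (whichever comes first"). Treatment-related SAEs after that point still count.
- **Treatment period (4.1.3).** The same cut applies to the summarised safety data, with 7 extra days for parameters collected by visit.

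Under Efficacy Follow-up (SAP 2.2), patients who stop drug for reasons other than progression are scanned every 12 weeks "for tumor assessment until disease progression, initiation of new anticancer therapy, withdrawal of consent, lost to follow-up, death, or the end of the study".

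**The concern.** The imputation protects the order of therapy and last dose. Rule 6 depends on the order of therapy and progression, which nothing protects. A patient may stop drug for toxicity, progress at a follow-up scan and then start new treatment. If the imputed start falls before the progression, the event is removed and the patient is censored at the previous scan. By plan, follow-up scanning ends when new therapy starts, so that scan is itself evidence that therapy had not begun.

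For safety, last dose + 1 is the earliest possible off-treatment day. The TEAE and treatment-period summaries then contain nothing after the last dose except treatment-related SAEs. This runs against the SAP's inclusive conventions elsewhere: a missing AE onset counts as a TEAE and missing causality counts as related (4.4.1), and a partial last-dose date is imputed late (5.1.2.4). TEAEs are part of the primary endpoint.

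**Working it through.** The SAP states no figure for this point, so there is nothing to reproduce. I applied its rules literally to illustrative patients. All patient dates are assumptions. I also assume that the imputed date is the one the analysis uses, since the SAP gives no other rule for it.

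**Inputs.** The three imputation rules and two bounds (5.1.2.6); rule 6 and the tie note (Table 5); months = days/30.4375 (4.2.1.5); TEAE window of 30 days (4.4.1).

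**Formulas.** PFS = (PD or censoring date − first dose + 1)/30.4375. Post-dose window = min(30, therapy start − 1 − last dose).

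First dose is 3 January 2022 (day 1). The last adequate scan before therapy is day 57 (28 February) in every case except D, where it is 20 June (day 169).

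| Case | Therapy date recorded | Last dose | PD | Assumed true start | Imputed start | PFS under SAP | PFS, true dates | Window, SAP / true (days) |
|---|---|---|---|---|---|---|---|---|
| A | nothing | day 70 | day 154 | day 161 | day 71 | censored, 57/30.4375 = 1.87 | event, 154/30.4375 = 5.06 | 0 / 30 |
| B | nothing | day 60 | day 57 | day 75 | day 61 | event, 1.87 | event, 1.87 | 0 / 14 |
| C | March | 2 Mar | 20 Mar (day 77) | 28 Mar | 15 Mar | censored, 1.87 | event, 77/30.4375 = 2.53 | 12 / 25 |
| D | year only | 20 Feb | 10 Sep (day 251) | 20 Sep | 1 Jul | censored, 169/30.4375 = 5.55 | event, 251/30.4375 = 8.25 | 30 / 30 |
| E | March | 25 Feb | 10 Mar (day 67) | 3 Mar | 15 Mar | event, 67/30.4375 = 2.20 | censored, 1.87 | 17 / 5 |
| F | March | 15 Mar | 14 Mar | 30 Mar | 15 Mar | event, 2.33 | event, 2.33 | −1 / 14 |
| G | March | 20 Mar | 14 Mar | 30 Mar | 21 Mar (raised) | event, 2.33 | event, 2.33 | 0 / 9 |

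- **A, C and D** lose a true event. In A the gap between scans is 154 − 57 = 97 days, below the SAP's 126-day limit, so the missed-visit rule is not the cause.
- **B** keeps its event because PD precedes last dose + 1, but still loses its window.
- **E** errs the other way: a patient who should be censored becomes an event, and the window is too long.
- **F** shows a gap in the floor. An imputed date equal to the last-dose date is not earlier than it, so it is not raised, and the last dosing day itself falls outside the window.
- **G** shows that a partial date can also reach 0 days, through the floor.

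**Are the midpoints early?** With a uniform true date, the 15th is early in 15/30 = 50.0% to 16/31 = 51.6% of cases and late in 14/31 = 45.2% to 14/30 = 46.7%. July 1st is early in 183/365 = 50.1% and late in 181/365 = 49.6%.

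**How often would the 15th precede PD?** Take a 31-day month with the day missing, last dose before the 15th, and all ordered pairs (PD, then therapy) equally likely. There are 31 × 30/2 = 465 pairs, and PD falls after the 15th in 16 × 15/2 = 120, or 25.8%.

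**Weight of one patient.** 1/36 = 2.8% to 1/27 = 3.7% of the planned enrolment. Over eight dose levels the average is 27/8 = 3.4 to 36/8 = 4.5 patients per level.

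**What drops out.** Protocol Table 1 places the EOT visit within 7 days (±3) after the last dose, with laboratory tests. Those taken after the last dose leave the summaries when the window is 0. The protocol supplied is Amendment 2, while the SAP cites Amendment 3, so the visit schedule is taken from Amendment 2.

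**The case against.** The strongest reply is that only the fully missing rule is extreme. The 15th and July 1st are ordinary midpoints, and case E shows that they can err the other way. That stands: a reader might infer that partial dates are imputed early in general, and they are not. The effect on events is still uneven. In the planned order (progression, then therapy), a late imputation changes nothing and one before PD deletes the event. Case E needs a scan after new therapy, which follow-up is designed to avoid. That design is a plan and not proof, since rule 6 exists because such scans can happen.

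Second, the affected group is narrow. Disease progression is itself a reason to stop drug, and a PD on or before the imputed start stays an event (case B and the tie note). That stands too, so the documents do not support a broad claim that PFS is inflated because most new therapy follows progression.

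Third, AE collection itself ends at new therapy (Protocol 8.2.1), and nothing vanishes from the report: all AEs and laboratory data are listed and follow-up deaths are tabulated (SAP 5.2.11.2 to 5.2.11.4). This limits the harm. However, collection follows the true start, so an AE recorded after the last dose suggests that the site did not think therapy had begun. The summaries, not the listings, carry the primary safety result.

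Fourth, PFS and DoR are secondary and descriptive, with no testing. That stands.

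**Conclusion.** The rule as written gives a wrong result in definable cases. A PD dated after an imputed therapy start is censored at an earlier scan, with no check that could prevent it. A fully missing date, or a partial date raised to last dose + 1, reduces the post-dose TEAE window from up to 30 days to 0. The summaries then lose post-dose AEs other than treatment-related SAEs, and off-treatment EOT laboratory results. The number of missing or partial dates is not given, so the total effect is unknown. One reclassified patient is 2.8% to 3.7% of the study and would show in a dose-level row.

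Three stronger inferences fail:

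- **That the AEs that led to stopping drug are lost.** They normally began on or before the last dose and remain TEAEs. What can be lost is a later worsening, because a change in severity is a new eCRF entry (Protocol 8.7.3), or an onset during a hold that became permanent.
- **That EOT ECGs are lost.** Protocol Appendix 1 schedules none at EOT.
- **That about half of same-month, post-dose progressions lose their event when the day is missing.** That treats the PD date as uniform over the month and ignores that therapy must follow within it. With both dates uniform and in order, the share is about 26%.

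**What to change.** Keep the midpoint rules and amend 5.1.2.6 as follows:

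- **(a) Progression bound.** Where the recorded part of the date allows, set the imputed start no earlier than first documented PD. The tie note then keeps the event. For a fully missing date, use the later of last dose + 1 and first PD or, without PD, the last study tumour scan. Cap at death or last known alive. Cases A, C and D return to events at 5.06, 2.53 and 8.25 months.
- **(b) Safety window.** State that an imputed therapy date does not shorten the 30-day TEAE window or the treatment period in 4.1.3.
- **(c) Floor.** Raise an imputed date that is on or before the reference end date, so that case F cannot arise.

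The cost is a few lines of SAP text and derivation code. The downside is that some progressions, responses or AEs that truly followed new therapy may be counted. Flag patients with imputed therapy dates in the listings so that readers can see them. Replacing the midpoints with the latest possible date is not needed; it would be a trade-off and not a correction.

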5.1.2.7. Primary Diagnosis Date and Metastatic Disease Diagnosis Date

When a partial date of primary diagnosis or a partial date of first metastatic disease diagnosis is reported, the below imputation rules will be used:

- If the date is completely missing, no imputation will be conducted;
- If only the day is missing, 15th day will be assigned;
- If both the day and the month are missing, then July 1st will be assigned.

Check that the imputed date is not on or after the informed consent date.

5.2. Analysis Methods

5.2.1. Patient Disposition

Summary of study disposition will be summarized:

- Number of patients who signed the informed consent
- Number of screen failures and reason for screen failures
- Number of patients who received study treatment

Based on safety analysis set, the following will be summarized by dose level/total and disease type:

- Patients still on study treatment
- Number and percentage of patients who discontinue the study drug
- Reason for study drug discontinuation
- Number of patients still on study
- Number and percentage of patients who discontinue the study
- Reasons for discontinuation of the study-

A separate table will be presented to show the patients included in each analysis set and proper reasons for exclusion from an analysis set.

Patient's discontinuation status and inclusion in analysis sets will be also listed.

5.2.2. Protocol Deviations

Major Protocol deviations will be summarized descriptively (frequency and percentage) for patients with at least one major protocol deviation by protocol deviation categories. A patient with multiple protocol deviations under the same category will be counted once per deviation category. The protocol deviation summary is based on the safety analysis set.

In addition, all protocol deviations will be presented in a by-patient listing.

5.2.3. Demographic and Other Baseline Characteristics

For the safety analysis set, demographic and other baseline characteristics, such as age (years) at informed consent date, age groups (<65 years, ≥65 years), gender, child bearing potential (if female), race, ethnicity, region (North America, and Europe), country, baseline height (cm), baseline weight (kg), baseline BMI (kg/m^2) calculated as $\text{baseline weight (kg)} / [\text{baseline height (m)}]^2$, BMI category (<18.5, ≥18.5 and <24, ≥24 kg/m^2), and baseline ECOG status, will be summarized and listed.

5.2.4. Disease Characteristics

Oncology history will be summarized descriptively by dose/disease cohorts and overall for the safety analysis set for the following:

- Diagnosis

- Time (months) since First Diagnosis of disease: it is calculated as (date of first study treatment administration – date of first diagnosis of disease + 1)/30.4375
- IDH Mutation Status
- Anatomical location of Primary tumor
- Time (months) since Diagnosis of Locally advanced/metastatic disease (months) : it is calculated as (date of first study treatment administration – date of diagnosis of metastasis disease + 1)/30.4375;
- Prior Oncology Treatments (Prior Anti-cancer Medication, Prior Anti-cancer Radiotherapy, Prior Anti-cancer Procedures)

In addition, oncology history data will be presented in a by-patient listing.

5.2.5. Medical History

The conditions/diseases from medical history are those conditions/diseases that stopped prior to the study entry. Medical history will be coded to SOC and PT using MedDRA version 27.1.

The number and percentage of patients with any past medical/surgical history within each SOC and PT will be provided by dose/disease cohorts and overall on the safety analysis set. The number and percentage of patients with any ongoing medical history will be summarized.

A patient will only be counted once within a particular SOC (PT) even if he/she has multiple conditions/diseases in the same SOC (PT).

Each summary will be ordered by descending order of incidence of SOC according to total column and PT within each SOC. If the frequencies tie, an alphabetic order will be applied.

In addition, medical history data will be presented in a by-patient listing.

5.2.6. Prior and Subsequent Anti-cancer Therapy

Prior and subsequent anti-cancer therapy, including medication, radiotherapy, and procedure or surgery, will be summarized descriptively for the safety analysis set.

5.2.6.1. Anti-cancer Medication

Prior anti-cancer medications are defined as those taken by the patient prior to the administration of study drug. Subsequent anti-cancer medications are defined as those taken by the patient after the discontinuation of the study drug.

Prior and subsequent anti-cancer medications will be coded to ATC therapeutic group (i.e. ATC Level 2) and PT using the WHO-DD Version Global B3 Sep 2024.

The prior anti-cancer medications will be summarized by presenting the number and percentage of patients by PT and ATC. Patients taking the same medication multiple times will only be counted once for that PT or ATC. Each summary will be ordered by descending order of incidence of ATC according to total column and PT within each ATC. If the frequencies tie, an alphabetic order will be applied.

Similarly, the subsequent anti-cancer medications will be summarized.

All prior and subsequent anti-cancer medications will be presented in a by-patient listing.

5.2.6.2. Anti-cancer Radiotherapy

Prior anti-cancer radiotherapy is defined as those taken by the patient prior to the administration of study drug.

Subsequent anti-cancer radiotherapy is defined as those taken by the patient after the discontinuation of the study drug.

The number and percentage of patients with at least one prior anti-cancer radiotherapy will be summarized by anatomical site.

Similarly, the subsequent anti-cancer radiotherapy will be summarized by anatomical site.

All prior and subsequent anti-cancer radiotherapy will be presented in a by-patient listing.

5.2.6.3. Anti-cancer Procedure or Surgery

Prior anti-cancer procedure or surgery are defined as those taken by the patient prior to the administration of study drug. Subsequent anti-cancer procedure or surgery are defined as those taken by the patient after the discontinuation of the study drug.

Prior and subsequent anti-cancer procedure or surgery will be coded to SOC and PT using MedDRA 27.1 or higher.

The prior anti-cancer procedure or surgery will be summarized by presenting the number and percentage of patients by PT and ATC(i.e. ATC Level 2). Patients taking the same medication multiple times will only be counted once for that PT or ATC. Each summary will be ordered by descending order of incidence of ATC to total column and PT within each ATC. If the frequencies tie, an alphabetic order will be applied.

Similarly, the subsequent anti-cancer procedure or surgery will be summarized.

All prior and subsequent anti-cancer procedure or surgery will be presented in a by-patient listing.

5.2.7. Prior and Concomitant Medications

Prior and concomitant medications (CMs) will be coded to ATC therapeutic group (i.e. ATC Level 2) and PT using the WHO-DD Version Global B3 Sep 2024.

Medications taken and stopped prior to the first dose of study treatment are denoted “Prior”. Medications taken prior to the first dose of study treatment and continuing beyond the first dose of study treatment or those medications started on or after the first dose of study treatment but no later than 30 days after the last dose are denoted “Concomitant”. Medication with start date/time being partially or completely missing will be assumed to be concomitant if it cannot be definitely shown that the medication did not occur during the treatment period.

The prior medications will be summarized by presenting the number and percentage of patients by PT and ATC. Patients taking the same medication multiple times will only be counted once for

that PT or ATC. Each summary will be ordered by descending order of incidence of ATC according to total column and PT within each ATC. If the frequencies tie, an alphabetic order will be applied.

Similarly, the concomitant medications will be summarized.

All prior and concomitant medications will be presented in a by-patient listing.

